**Adjunctive Nitrous Oxide during ED propofol sedation in adults,
a pilot study.**

NCT02410707

Version: 7/1/14

Investigator(s): [name], DO; [name], DO; [name]; [name], CCRC

Objectives

To describe the safety and efficacy of adjunctive nitrous oxide pre-propofol administration for analgesia and pre-procedure anxiolysis during ED procedural sedation and analgesia in adults.

Background

Specific Aims

To measure the rates of hypoxia and respiratory depression requiring a physician intervention in adult patients receiving 50% demand valve nitrous oxide pre-propofol administration during ED procedural sedation and analgesia. Secondary aims include patient, nursing, and physician post procedure satisfaction scores, Ramsay sedation scores, total propofol dose given, length of time spent using nitrous oxide, patient recall of procedure.

Significance

Procedural sedation is the use of sedative, analgesic, and/or dissociative agents to relieve anxiety and pain associated with diagnostic and therapeutic procedures. Propofol has become one of the most commonly used agents for ED procedural sedation.^{1,2} Propofol crosses the blood-brain barrier rapidly. The drug takes effect within approximately 40 seconds, and its

duration of action is approximately six minutes^{2,3} Multiple randomized trials and prospective observational studies have found propofol to be safe and effective for PSA in the emergency department^{3,4,5}. Propofol acts as a sedative and amnestic, but provides no analgesia.

A possible approach is pretreatment with short-acting opioids (eg, fentanyl). Unfortunately, the addition of opioids increases the likelihood of respiratory complications. As an example, fentanyl at a dose of 1.5 mcg/kg increases the risk of respiratory depression. In another study, patients given both alfentanil and propofol required stimulation to induce respiration more often than those given only propofol.⁷ Another alternative to pretreatment with short-acting opioids is to use sub-dissociative doses of ketamine (0.3 mg/kg). Ketamine appears to provide comparable analgesia with less risk of respiratory depression. However, there is no literature that has shown that there is a decreased risk of respiratory depression than with propofol.⁸

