2. Inclusion and Exclusion Criteria

- i. Inclusion criteria: All spontaneously breathing subjects, 18 years of age and older, with an American Society of Anesthesiologists (ASA) Physical Status Classification 1 or 2, who will be receiving sedation for an ED procedure.

Written informed consent will be obtained from all subjects.

- ii. Exclusion criteria: Subjects with underlying conditions that could affect ventilation, perfusion, or metabolism including intubated subjects, subjects with clinical signs of cardiopulmonary instability, major trauma, shock, sepsis, ASA class 3, 4, and 5. Also those unable to provide informed consent, nursing home residents, age less than 18 years, non English speaking, pregnant women, subjects under police custody, or physician discretion.

3. Study Endpoints

- i. Primary:

1. ETCO₂ measured q 20 milliseconds seconds
2. SpO₂ measured q 20 milliseconds seconds

- ii. Secondary Endpoints

1. A baseline reading of the vital signs (heart rate, respiratory rate, peripheral SaO₂ and ETCO₂)
2. Physician interventions (verbal or physical stimulation, airway repositioning, additional oxygen, positive pressure ventilation, endotracheal intubation)
3. Level of sedation (Ramsay Score)
4. Patient Demographics
5. Patient recall of procedure
6. Total propofol dose
7. Total elapsed time of nitrous oxide use
8. Patient and physician procedure satisfaction score

4. Procedures Involved in the Research

Initial medical assessment will be made in accordance with established clinical procedures, including the history, physical examination, and vital signs. If by clinical assessment the patient meets eligibility criteria, then they will be approached by a research associate for enrollment in the study. After informed consent is obtained and prior to starting the sedation, standard vital sign monitoring will be placed on the patient (electrocardiogram, non-invasive blood pressure monitoring, pulse oximetry, and capnography). Level of consciousness will be determined using the modified Ramsay scale, which will be assessed at baseline. The Capnostream 20 ETCO₂ monitor will be used as the primary device to measure ETCO₂, with a nasal cannula capable of delivering supplemental oxygen and measuring ETCO₂ (Oridion Medical, Needham, MA).

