Vital signs will be flagged electronically when a physician intervenes for clinical respiratory depression. Respiratory depression will be defined as peripheral SaO₂ below 92%, ETCO₂ level above 50, a rise or decrease of 10% above or below baseline, the loss of the ETCO₂ waveform for more than 15 seconds. Level of consciousness will be determined using the modified Ramsay scale, which will be recorded at baseline and at the point of deepest sedation. Once the procedure is complete, and the patient is deemed back to their mental status baseline, they will fill out a post procedure satisfaction questionnaire, and a 100mm VAS scale. They will be asked about procedure recall. The physician will also fill out a post procedure questionnaire.

5. Data Management

A standardized data collection form will be used to collect clinical data and a USB drive to collect electronic vital sign data. Initial data gathered will include age, gender, weight, and baseline vital signs (BP, HR, RR, peripheral SpO₂, and ETCO₂). Other information collected will be the elapsed time of nitrous oxide use, start time (when protocol was given), time (when patient returns to baseline), elapsed time in seconds under sedation (from start time to end time),

medications administered, repeated doses and times for every administered medication, total dose of each medication administered, adverse events, and interventions aimed at correcting respiratory depression. Level of consciousness using the modified Ramsay scale will also be recorded at baseline and at set intervals during sedation.

The electronic monitoring data will be continuously recorded into the USB drive throughout the sedation and recovery periods. The Capnostream 20 ETCO₂ monitor (Oridian Medical, Needham, MA) is capable of sampling and recording ETCO₂ and pulse SaO₂ every 5 seconds. A patient identifier will be recorded to link the subject and the electronic monitoring data without compromising his/her confidentiality. At the completion of the sedation, all device data will be transmitted to a password-protected Excel/SPSS spreadsheet for analysis. The research associate is responsible for recollection and storage of the data. Only the primary investigators, the study coordinator, and the research associates will have access to such.

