To assess these outcomes, we will download electronic data from each sedation into a Microsoft Excel database, checked and adjudicated any discrepancies with research associate notations, and generate a graph of the subject's sedation with the X-axis showing time and the Y-axis depicting ETCO₂, SpO₂, respiratory rate, and heart rate. Electronic time stamps noted propofol administration, procedure initiation and completion, adverse events, and physician interventions.

Before study blinding is broken, three investigators will evaluate each graph to code the presence or absence of cerebral hypoxia, peripheral hypoxia and respiratory depression. We will disqualify graphs if they had >35% data loss, unless all three evaluators agreed that there was unequivocal evidence of hypoxia (cerebral and or peripheral) and/or respiratory depression.

6. Withdrawal of Subjects

Participation is voluntary. Subjects may withdraw from this study at any time. If this is the case their data will be deleted. We will record the number of patients that withdraw. Subjects may be withdrawn without their consent if the electronic data cannot be recorded.

Statistical Plan

1. Sample Size Determination

As this is a pilot, prospective, observational trial, no power calculation will be used to measure a difference. In previous propofol studies, approximately 10-30% of patients develop hypoxia, and approximately 50% of patients meet criteria for respiratory depression. Thus, we believe enrolling 100 patients in this observational trial will allow for approximation of any correlations that are measured.

2. Statistical Methods

All clinical observations and demographic data will be summarized using medians with range or means with standard deviations as appropriate. Rate of detection of respiratory depression and hypoxia and timing of these events for each instrument (near-infrared spectroscopy, pulse oximetry, capnography) will be summarized descriptively. Associations among SaO₂, and ETCO₂ will be estimated using spearman's rank correlation coefficient, using within-cluster resampling algorithm. This will allow for estimation of the marginal correlation in the presence of clustered data. Correlations not involving repeated measures data will be estimated with Spearman's rank correlation coefficient. All analysis will be conducted using SPSS software (IBM, Armonk, NY).

Risks to Subjects

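### No planned analysis gives the primary aim's rate of events requiring a physician intervention, and the data-loss rule makes the denominator depend on outcome

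*Combined protocol and SAP*

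**What the plan says.** Specific Aims sets the target: "To measure the rates of hypoxia and respiratory depression requiring a physician intervention in adult patients". Total propofol dose, satisfaction, sedation scores, nitrous oxide time and recall are secondary aims.

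Study Design, 3. Study Endpoints does not carry that target over. The primary endpoints are two signals, "ETCO₂ measured q 20 milliseconds seconds" and the same for SpO₂. The secondary list holds "Physician interventions (verbal or physical stimulation, airway repositioning, additional oxygen, positive pressure ventilation, endotracheal intubation".

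Study Design, 4. Procedures defines the event by the monitor: "Respiratory depression will be defined as peripheral SaO₂ below 92%, ETCO₂ level above 50", then "a rise or decrease of 10% above or below baseline, the loss of the ETCO₂ waveform for more than 15 seconds". The definition has no intervention component. Interventions are captured all the same: "Vital signs will be flagged electronically when a physician intervenes for clinical respiratory depression". Data Management collects "adverse events, and interventions aimed at correcting respiratory depression" and puts intervention time stamps on each subject's graph.

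Data Management then has three investigators code each graph for cerebral hypoxia, peripheral hypoxia and respiratory depression. A graph with more than 35% data loss is disqualified, unless all three agree that one or more of these is clearly present. Under 6. Withdrawal, the data of subjects who withdraw are deleted (their number is recorded), and subjects whose electronic data cannot be recorded may be removed.

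Statistical Methods plans "Rate of detection of respiratory depression and hypoxia and timing of these events for each instrument (near-infrared spectroscopy, pulse oximetry, capnography", described by instrument, together with Spearman correlations and a general summary of clinical observations by medians or means. No analysis set is named.

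**The concern.** Meeting a monitor threshold and needing a physician to act are different quantities. The aim is about the second, while the coding and the planned rates are about the first. An analyst who follows the plan as written would report detection rates by instrument and never compute the rate that the study was set up to measure. In a single-group safety pilot that rate is the main result.

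The denominator is a second problem. One hundred is an enrolment target. After enrolment, graphs can be disqualified and subjects removed, and whether a lossy graph stays depends on what it shows. A clearly event-free lossy graph has no route back. The reported rates can therefore move for reasons unrelated to nitrous oxide, and a reader cannot judge by how much unless the counts are given.

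**Working it through.** **Inputs from the documents.** n = 100 (Study Design). About 50% are expected to meet respiratory-depression criteria and 10-30% to develop hypoxia (Sample Size Determination). The plan gives no power or precision calculation, so there is no figure to reproduce. It gives no share of lossy graphs and no share of events that lead to an intervention. Those are assumptions below.

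**1. Does any planned step yield the aim's rate?**
- Graph coding gives event present or absent. It has no intervention code.
- Statistical Methods gives detection rate and timing by instrument. It makes no link to an intervention.
- The summary of clinical observations could take in interventions, but by medians or means. It gives no proportion and no link to an event.
- Flags, time stamps and the intervention record are collected, but no analysis joins them to the coded events.

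**2. How far apart are the two quantities?** Intervention-qualified rate = 0.50 × q, where q is the share of respiratory-depression cases with an intervention. ASSUMPTION q = 0.2, 0.5, 0.8: the rate is 10%, 25% or 40%, against 50% on criteria alone. This shows the size of the ambiguity and is not a forecast.

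**3. The exception against dropping all lossy graphs.** Let x of n non-lossy graphs be positive, and let m lossy graphs be kept, y of them positive. The rate is (x + y)/(n + m), which exceeds x/n only when y/m exceeds x/n.
- *Any event:* every kept graph has one, so y/m = 1 and the rate cannot fall.
- *One particular event:* a graph kept for respiratory depression may be negative for hypoxia or for intervention, so y/m can lie anywhere from 0 to 1.

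ASSUMPTION: 20 of 100 graphs are lossy, loss is unrelated to events, hypoxia (30%) is nested in respiratory depression (50%), and all 10 lossy respiratory-depression graphs are kept.

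| Rate | All lossy dropped | With exception |
|---|---|---|
| Respiratory depression | 40/80 = 50.0% | (40 + 10)/90 = 55.6% |
| Hypoxia, readable in kept graphs | 24/80 = 30.0% | (24 + 6)/90 = 33.3% |
| Hypoxia, not readable in kept graphs | 24/80 = 30.0% | (24 + 0)/90 = 26.7% |

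The intervention-qualified rate behaves the same way. With q = 0.5, 20/80 = 25.0% becomes (20 + 5)/90 = 27.8% if 5 of the 10 kept graphs have a linked intervention, and 20/90 = 22.2% if none has.

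**4. The exception against the true rate.** Loss of the ETCO₂ waveform is itself a respiratory-depression criterion, so data loss may be linked to events. For a single event with true rate p, lossy shares fe (event graphs) and fn (non-event graphs), and share k of lossy event graphs kept:

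observed = p(1 − fe + fe·k) / [p(1 − fe + fe·k) + (1 − p)(1 − fn)]

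ASSUMPTION fe = 0.30, fn = 0.10, with p = 0.50:
- k = 0: 0.350/(0.350 + 0.450) = 43.8%
- k = 0.5: 0.425/(0.425 + 0.450) = 48.6%
- k = 1: 0.500/(0.500 + 0.450) = 52.6%

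Break-even is k = 1 − fn/fe = 0.67. The sign depends on quantities that the plan does not give.

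**5. Scale.** Exact (Clopper-Pearson) 95% intervals are 21.2-40.0% for 30/100 and 39.8-60.2% for 50/100. The shifts in steps 3 and 4 at true rates of 30% and 50% lie inside them.

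**6. What the recorded interventions can recover.** ASSUMPTION: 20 of 100 graphs are unreadable, there are 20 intervention-qualified events in the other 80, and 5 of the 20 unreadable subjects have a recorded intervention. From graphs alone the bounds are 20/100 to (20 + 20)/100, or 20-40%. Using the recorded interventions, they are 20/100 to (20 + 5)/100, or 20-25%.

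**The case against.** The best defence is that this is a single-group descriptive pilot. Interventions are a listed endpoint, all clinical observations are to be summarised, and Specific Aims already says which rate matters. The loss share is unknown, and the illustrated shifts are smaller than sampling error. Exact intervals and bounds are partly a matter of preference in such a study.

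Much of that stands, and it rules out several stronger readings that a reader might infer:
- *That the aim cannot be answered.* The flags, time stamps and intervention records are collected, so the gap is in the analysis.
- *That the choice of main result is wholly open.* Specific Aims puts the intervention-qualified rate first and names the others as secondary. The endpoint list and Statistical Methods then fail to follow it.
- *That the exception always inflates the rates.* It is triggered by any of three findings, so this holds only for the any-event rate, and only against dropping all lossy graphs.
- *That hypoxia is simply the SaO₂ criterion.* Cerebral hypoxia is coded separately and near-infrared spectroscopy is named in Statistical Methods, yet that instrument is not in the study procedures.

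The defence does not supply a joint proportion. Nor does the small size excuse the data-loss rule: sampling error shrinks with more patients, while a shift built into the inclusion rule does not.

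**Conclusion.** The concern holds in two parts. First, no planned analysis yields the per-patient rate of events requiring a physician intervention that the primary aim names. This rests on the text alone. Second, inclusion of graphs with more than 35% loss depends on outcome. Under the assumptions in step 3, respiratory depression moves from 50% to 55.6%, and hypoxia from 30% to 33.3% or 26.7%. If loss is linked to events as in step 4, a true 50% reads between 43.8% and 52.6%. The direction against the true rate is unknown. The lossy, kept and intervention shares are all assumed, and the sizes illustrate the rule rather than predict its effect. Both parts should be fixed before any graph is coded, and both can be.

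**What to change.** 1. **Name the rates.** Before any graph is coded, make primary the per-patient proportion with respiratory depression and a flagged intervention, and the per-patient proportion with hypoxia. State whether the intervention qualifier applies to hypoxia, and whether cerebral hypoxia counts. Report respiratory depression on criteria alone as secondary. Give each an exact 95% CI.
2. **Use one outcome-independent denominator for every rate.** Take all subjects who received nitrous oxide and propofol and did not choose to withdraw. Keep disqualified graphs and recording failures in as unreadable.
3. **Report the counts.** Give the numbers of graphs disqualified, graphs kept under the exception and recording failures, beside the withdrawal count already planned.
4. **Give bounds.** Count unreadable subjects first as non-events and then as events. For the intervention-qualified rate, narrow the bounds by treating an unreadable subject with no recorded intervention as a non-event. Show the result without the exception as a descriptive check, not as an unbiased estimate.

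**Cost.** Some protocol wording and slightly more descriptive analysis. No new patients or data are needed, provided the data collection form (Attachment B, not shown) holds interventions for subjects with unreadable graphs; this should be checked. Bounds for hypoxia may be wide if many graphs are lost, because the intervention record does not narrow them.
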